2.3.2 Safety Set

The Safety Set (SS) will include all patients enrolled in the CRAD001M2305 study who have at least one-post CRAD001M2305 baseline safety assessment. It should be noted that all patients enrolled in the CRAD001M2305 study have been exposed to everolimus in the parent study CRAD001M2301 (and may or may not continue receiving commercial everolimus while on CRAD001M2305).

The safety set will be the population used in the assessments of safety, such as adverse events (AEs) and everolimus exposure.

2.4 General statistical methodology

2.4.1 Center pooling

All study centers will be combined for the analysis. Due to the expected small size of centers, no center effect will be assessed.

2.4.2 Analysis of percentage rates

The primary objective of this study is to report the effect of everolimus on height, BMI and sexual development (using Tanner Stages) in children and adolescents with TSC-associated SEGA who are taking everolimus or have taken everolimus.

The rates of sexual maturation will be described as the percentage of patients who have reached Tanner Stage V by age 16 (for females) or age 17 (for males).

2.4.2.1 Hypothesis and test statistic

No statistical tests are planned for any of the percentage rates.

2.4.2.2 Confidence interval for percentage rates

Endpoints will be summarized in terms of percentage rates with exact 95% confidence intervals. An *exact binomial confidence interval* [Clopper & Pearson, 1934] will be used, implemented using SAS procedure FREQ with the EXACT statement for one-way tables.

2.4.3 Time-to-event analyses

This section presents the general methodology used to analyze time-to-event variables, e.g., age at which each Tanner Stage will be reached, age at thelarche (females), age at menarche (females) and age at adrenarche (males).

2.4.3.1 Kaplan-Meier estimates

An estimate of the time-to-event function will be constructed using the *Kaplan-Meier (product-limit) method* as implemented in the procedure LIFETEST with the METHOD=KM option. Median time-to-event will be obtained along with a 95% confidence interval calculated from the procedure LIFETEST using the method of [Brookmeyer & Crowley, 1982].

Kaplan-Meier (KM) estimates of the time-to-event function with 95% confidence intervals every 12 months, where 12 months is defined as 365.25 days, will be presented. The confidence

intervals will be constructed using Greenwood's formula [Collett, 1994] for the standard error of the KM estimate. The log-log transformation of the survivor function [Kalbfleisch and Prentice, 1980] will be used in order to ensure that the confidence limits remain in the interval [0, 1]. The log-log transformation is implemented in the LIFETEST procedure using the option CONFTYPE=LOGLOG.

3 Statistical methods used in reporting

3.1 General presentation of descriptive summaries

Qualitative data (e.g., gender, race, etc.) will be summarized by appropriate descriptive statistics (i.e. frequencies and percentages); a missing category will be included as applicable. Percentages will be calculated using the number of patients in the relevant population or subgroup as the denominator.

Quantitative data (e.g., age, body weight, etc.) will be summarized by appropriate descriptive statistics (i.e. mean, standard deviation, median, 25th and 75th percentiles, minimum, and maximum).

3.2 Background and demographic characteristics

For CRAD001M2305 patients, all data described below will be pooled with the corresponding data from Study CRAD001M2301.

Demographic and other baseline characteristics will be described by study (CRAD001M2305 and TOSCA), side by side, on the two Full Analysis Sets (FAS and FAS Puberty).

The summary table will include age, sex, race, weight, height, body mass index (BMI) at baseline.

Age will be summarized by age category (≤ 12 , >12) for both the studies.

All demographic and background data will be listed.

3.3 Protocol deviation summaries

For CRAD001M2305 patients, all protocol deviations which occurred during the CRAD001M2305 study will be analyzed, The number (%) of participants with any protocol deviation will be tabulated by deviation category, PDs that are pandemic related will be summarized by relationship to COVID-19.

All protocol deviations will be listed (as specified in the VAP documents) using the FAS population.

3.4 Grouping for analysis

The number and percentage of patients in each analysis population will be summarized.

3.5 Patient disposition

For the CRAD001M2305 patients, the FAS will be used for the patient disposition summary tables and listings. Information from the CRF page “End of Treatment” and “End of Study” CRAD001M2305 study will be used to provide a summary showing:

- Number (%) of patients who started/ongoing commercial everolimus
- Number (%) of patients with Treatment discontinuation and their discontinuation reason
- Number (%) of patients with study discontinuation and their discontinuation reason

3.6 Study treatment

For CRAD001M2305 patients, all data described below will be pooled with the corresponding data from Study CRAD001M2301 and will be summarized using the safety set.

The participation in this study does not require the administration of everolimus. In such cases in which the patient was taking everolimus, data collection (such as therapeutic drug trough level, duration of everolimus interruptions and everolimus prescribed dose) will only be recorded, when available.

For patients in Study CRAD001M2305, the duration of everolimus exposure and cumulative everolimus dose will be described using descriptive statistics on the Safety Set.

The total duration of everolimus exposure will be calculated as the total duration of everolimus exposure received while on Study CRAD001M2301 plus the total duration of (commercially supplied) everolimus exposure reported in Study CRAD001M2305.

Similarly, the cumulative dose of everolimus will be calculated as the cumulative everolimus dose received while on Study CRAD001M2301 plus the cumulative everolimus (commercially supplied) dose reported in Study CRAD001M2305.

All exposure data will be listed.

3.7 Concomitant therapy

For CRAD001M2305 patients, all data described below will be pooled with the corresponding data from Study CRAD001M2301. Concomitant medication ongoing at the time of enrollment in CRAD001M2305 and during the study will be summarized. Medications used at time of CRAD001M2301 will be listed.

Concomitant therapy will be described using the safety set.

Concomitant therapy is defined as all interventions (therapeutic treatments and procedures) besides everolimus that were administered to a patient preceding or coinciding with everolimus intake.

Concomitant medications entered into the database will be coded using the WHO Drug Reference List to allow for categorization by preferred term (PT). In addition to categorizing medication data by PT, drugs are classified according to their Anatomical Therapeutic Chemical (ATC) classification in order to present and compare how they are being utilized. The ATC classification allows for a summary of medications by a high-level common drug class.

Concomitant medications and significant non-drug therapies taken concurrently with everolimus will be listed and summarized by ATC class and PT by means of frequency counts and percentages. These summaries and listings will include medications starting on or after the start date of everolimus, or medications starting prior to the start date of everolimus and continuing after the start date of everolimus. Medications starting more than 30 days after the last day of everolimus will be only listed.

3.8 Primary objective

The primary objective of this study is to report the effect of everolimus on height, BMI and sexual development (using Tanner Stages) in children and adolescents with TSC-associated SEGA who are taking everolimus or have taken everolimus.

To monitor the growth and the development of pediatric patients the following measurements will be performed annually:

- Height
- Weight
- Tanner Stage
- LH, FSH, and estrogen levels for female patients (for the CRAD001M2305 study, collected only for patients of 10 years old or older during the study)
- LH, FSH, and testosterone levels for male patients (for the CRAD001M2305 study, collected only for patients of 10 years old or older during the study)

3.8.1 Height and BMI

For CRAD001M2305 patients, all data described below will be pooled with the corresponding data from Study CRAD001M2301.

The height standard deviation score (SDS) will be calculated based on height data collected during the study and published reference height information. The height SDS (also called z-score) will be computed for a particular patient at each time point. The same approach will be used to compute BMI SDS. BMI will be calculated as weight (in kg) / squared height (in m). The z-scores will allow identification of potential outliers.

SDS will be calculated using the current formula provided by the WHO as follows:

1. Calculate $z_{ind} = \frac{\left(\frac{X}{M}\right)^L - 1}{LS}$
2. If $|z_{ind}| \leq 3$, $SDS = z_{ind}$
If $z_{ind} > 3$, $SDS = 3 + (X - SD3pos) / SD23pos$
If $z_{ind} < -3$, $SDS = -3 + (X - SD3neg) / SD23neg$

where:

- X is height in centimeters or BMI in kilograms/m²,
- L , M and S are height or BMI-, sex- and age-specific reference values from the WHO Growth Charts.
- $SD3pos$ is the cutoff 3SD calculated by the LMS method:
 $SD3pos = M * (1 + LS*3)^{1/L}$

- $SD3neg$ is the cutoff -3SD calculated by the LMS method:
 $SD3pos = M * (1 + LS*(-3))^{1/L}$
- $SD23pos$ if the difference between the cutoffs 3SD and 2SD:
 $SD23pos = M * (1 + LS*3)^{1/L} - M * (1 + LS*2)^{1/L}$
- $SD23neg$ if the difference between the cutoffs -2SD and -3SD:
 $SD23neg = M * (1 + LS*(-2))^{1/L} - M * (1 + LS*(-3))^{1/L}$

Height-for-age and BMI-for-age L, M and S reference values for boys and girls are available under [<http://www.who.int/childgrowth/standards/en/>] (for patients aged between 0 to 5 years old) and [<http://www.who.int/growthref/en/>] (for patients aged between 5 to 19 years old). These correspond to the latest available international references available at the time of this protocol and described in the 2007 Bulletin of the World Health Organization (Mercedes de Onis et al 2007). However, these references may be revised according to new available standards at the time of the analysis.

The age category immediately above the patient's exact age should be used. SDS is actually a Z score that measures the distance from the population mean in units of standard deviations. That is, $SDS < 0$ refers to values lower than the population mean, and for example $SDS \leq -1.645$ refers to values in the lowest 5%. (The usual percentile more commonly used in the clinical practice can be derived from the Z-score by a normal distribution).

The time-course of height and BMI SDS will be summarized, side by side, on the FAS of the studies CRAD001M2305 and TOSCA using descriptive statistics by year since the enrollment date (for TOSCA patients) or since the start of everolimus (for CRAD001M2305 patients). The counts and frequencies of patients with height and BMI SDS values lower than the 5th percentile (notably low) or higher than the 95th percentile (notably high) will be described on the FAS, overall and by region. The counts and frequencies by region will be provided if sufficient sample size observed within the region for CRAD001M2305 study.

The rate of height (respectively BMI) growth notable abnormality will be calculated as the rate of patients with a height $SDS < 5$ th percentile at the last time point where height is reported.

If the number of CRAD001M2305 patients is sufficient and if a high rate of notably height (respectively BMI) growth abnormality occurs, the relationship between the everolimus exposure and the height growth abnormality will be further explored as detailed below:

- The rate of height (respectively BMI) growth abnormality will be described in the different subgroups defined by the duration of everolimus exposure. These subgroups are described in the Section 3.12.
- The duration of exposure and the age at start of everolimus will be summarized using descriptive statistics in the subgroups of patients with and without a height (respectively BMI) growth abnormality.
- A logistic regression including the duration of exposure and the age at the start of everolimus as continuous covariates will also be used to further explore the relationship between the everolimus exposure and the height (respectively BMI) growth notable abnormality. Additional covariates (e.g. time normalized Cmin) might also be included in the model.

In addition, individual patient graphs for height and BMI over time will be provided for CRAD001M2305 patients.

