2.1.6.1 Growth data/ Endocrine data

Height and weight were collected at screening/baseline, every 4 weeks until Week 12, every 6 weeks until Week 24, every 12 weeks until EOT in the CRAD001M2301 study. The growth data (height and BMI) will be collected at the enrollment and every year until EOT in the CRAD001M2305 study. The growth data will be collected at the baseline and annually if available in the TOSCA study.

The endocrine data (LH, FSH, testosterone (in males) and LH, FSH, estrogen (in females)) will be collected in the CRAD001M2305 study at the baseline and then yearly, hence corresponding data will be pooled from CRAD001M2301 Study. The endocrine data will be collected in the TOSCA study at enrollment and annually if available.

Table 2-1 summarizes the time windows for Growth data/Endocrine data analyses, where windows are centered at every year after start of everolimus for CRAD001M2305 patients and every year after the enrollment date for TOSCA patients.

Table 2-1 Time windows for Growth data/ Endocrine data

Time Window	Planned Assessment Day		Time Window Definition	
	CRAD001M2305	TOSCA	CRAD001M2305	TOSCA
Baseline	Last available assessment on or before the start of everolimus in the parent study CRAD001M2301	First available assessment after the enrollment date	Before or on Treatment Day 1	Between Study Day 1 and Study Day 182
Year 1	Treatment Day 365	Study Day 365	Treatment Days 183 to 547	Study Days 183 to 547
Year 2	Treatment Day 730	Study Day 730	Treatment Days 548 to 913	Study Days 548 to 913
Year 3	Treatment Day 1096	Study Day 1096	Treatment Days 914 to 1279	Study Days 914 to 1279
Year 4	Treatment Day 1461	Study Day 1461	Treatment Days 1279 to 1644	Study Days 1279 to 1644
Every year thereafter until the end of each study				

Growth data, if more than one assessment is done within the Baseline time window, the assessment closest to study day 1 (for TOSCA) or treatment day 1 (for CRAD001M2301) will be used; if two or more assessments are equidistant from day 1, then the mean value will be used. For all other time windows, the assessment closest to the planned assessment date will be used; if two or more assessments are equidistant from the planned date, then the mean value will be used.

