2.2 Data included in the analysis

This Study CRAD001M2305 is a long-term safety follow-up study and statistical analyses will be primarily descriptive for all endpoints. The planned statistical analysis is described in Section 10 of the protocol.

Data collected for the patients enrolled in this CRAD001M2305 study will be pooled with the corresponding data previously collected in the parent CRAD001M2301 study for the same patients, in particular, background information on the disease history, demographics and baseline characteristics, everolimus exposure, sexual and growth development data. This pooling will allow for the following:

- Obtaining baseline values collected in CRAD001M2301 before start of everolimus
- Calculating the whole exposure to everolimus for patients enrolled in the CRAD001M2305 study
- Considering the whole growth/development course over time from the start of everolimus.

The descriptive analyses of data from the CRAD001M2305 study and TOSCA registry will be presented, side by side, whenever similar data are collected in both studies. This is intended to facilitate the interpretation of the CRAD001M2305 results and help describe any potential impact of everolimus on growth and sexual development, in the TSC population, whose growth and sexual development independent of exposure to systemic mTOR inhibitors is not well characterized.

Table 2-2 summarizes the data which will be included in all the analyses described in the SAP.

Table 2-2 Data included in each analysis

Endpoints	Studies			Analysis Set
	CRAD001M2305	CRAD001M2301	TOSCA	
Baseline characteristics	X	X	X	FAS and FAS Puberty
Patient disposition	X			FAS
Protocol deviations	X			FAS
Concomitant therapy	X	X		Safety Set
Height and BMI	X	X	X	FAS
Tanner stage	X	X	X	FAS puberty
Endocrines	X	X	X	FAS
Adverse events	X	X		Safety Set
Age at menarche	X	X		Safety Set
Age at thelarche	X	X		Safety Set
Age at adrenarche	X	X		Safety Set
Potential delayed puberty	X	X		Safety Set
TAND checklist	X		X	FAS
Indirect comparison	X	X	X	FAS and FAS puberty

Endpoints	Studies			Analysis Set
	CRAD001M2305	CRAD001M2301	TOSCA	
Treatment exposure	X	X		Safety Set
Pharmacokinetics	X	X		Safety Set

In order to ensure all data in the trial is captured, the cut-off date for final analysis will be fixed to the date of the last patient last visit. For the purpose of the final analysis, all tables, figures and listings (TFLs) described in this SAP as well as in TFL shells will be produced.

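### The growth-abnormality rate uses the last height only, and no planned growth summary pairs a child's pre-everolimus value with the later one

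*SAP*

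**What the plan says.** SAP 3.8 gives the aim: "The primary objective of this study is to report the effect of everolimus on height, BMI and sexual development". SAP 3.8.1, in the same words as Protocol 10.4.1.2, then defines the abnormality measure: "The rate of height (respectively BMI) growth notable abnormality will be calculated as the rate of patients with a height" SDS under the 5th percentile at the last time point with a height. Baseline status plays no part in it.

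The pre-drug values exist. SAP 2.2 gives as one reason for pooling with the parent study: "Obtaining baseline values collected in CRAD001M2301 before start of everolimus". SAP 2.1.6.1 confirms the collection: "Height and weight were collected at screening/baseline, every 4 weeks until Week 12".

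The plan shows baseline in these places:

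- **Baseline table (SAP 3.2):** "The summary table will include age, sex, race, weight, height, body mass index (BMI) at baseline". These are raw measurements, as a group summary.
- **Yearly SDS summary (SAP 3.8.1):** Table 2-1 has a Baseline window, defined for CRAD001M2305 as "Last available assessment on or before the start of everolimus in the parent study CRAD001M2301". Each window is summarised separately.
- **Counts of notably low and notably high SDS (SAP 3.8.1):** the time point is not stated, so these may or may not include baseline.
- **Individual displays:** "individual patient graphs for height and BMI over time will be provided for CRAD001M2305 patients" (SAP 3.8.1). The Protocol summary also promises growth charts for each patient.

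The only analysis that names baseline height and BMI abnormality is the propensity-score comparison with TOSCA (SAP 3.9.3). SAP 4.2 sets it aside as not meaningful with 15 patients.

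**The concern.** The rate is a prevalence at the last visit. It comes out the same whether the flagged children were short before the first dose or became short on the drug, and for a study reporting the effect of everolimus on growth that difference matters. The parent-study baseline was pooled in partly so that the two could be told apart. Yet neither document specifies a shift table, a newly-low rate or a paired change in SDS for height or BMI. The exposure logistic regression in SAP 3.8.1 names only duration of exposure and age at start. It allows further covariates but does not name baseline SDS.

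With few children, one who was low from the outset changes the reported percentage visibly. The summary tables would not show which kind of case it was.

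**Working it through.** **Inputs from the documents.** N = 15 (SAP 4.2); expected abnormality rate 5–10% (SAP 3.13); cut-off SDS −1.645 (SAP 3.8.1); exact Clopper–Pearson 95% intervals (SAP 2.4.2.2). The number low at baseline is not given.

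**1. The plan's own figures.** The limits are the 2.5% quantile of Beta(x, n−x+1) and the 97.5% quantile of Beta(x+1, n−x).

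- 1/15 gives 0.002–0.319; SAP 4.2 prints (0.00, 0.32).
- 3/15 gives 0.043–0.481; SAP 4.2 prints (0.04, 0.48).
- 4/50 gives 0.022–0.192; SAP Table 3-1 prints (0.02, 0.19).

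These reproduce.

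**2. What the marginal counts leave open.** Let b children be low at baseline and 3 be low at the last visit, out of 15. The planned rate is 3/15 = 20% in every row. The number newly low can be anything from 3 − b to 3, among 15 − b children at risk.

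| Low at baseline (b) | Newly low, smallest | Newly low, largest |
|---|---|---|
| 0 | 3/15 (20%) | 3/15 (20%) |
| 1 | 2/14 (14%) | 3/14 (21%) |
| 2 | 1/13 (8%) | 3/13 (23%) |
| 3 | 0/12 (0%; CI 0–26%) | 3/12 (25%; CI 5–57%) |

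In the last row both marginal counts are fixed, yet the newly-low figure runs from 0% to 25%. Only a paired table settles it. Three low children is an illustration above the expected count (step 3). With 1 low at baseline and 1 low at the end, the choice is between 0/14 (CI 0–23%) and 1/14 (7%; CI 0–34%).

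**3. How many might be low before the drug.** Apply the plan's 5–10% to baseline, which is an assumption.

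- Expected number: 15 × 0.05 = 0.75 to 15 × 0.10 = 1.5.
- Chance of at least one: 1 − 0.95^15 = 0.54 to 1 − 0.90^15 = 0.79.
- Weight of one child: 1/15 = 6.7 percentage points.

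**4. What paired outputs could show.** Assume normal SDS with SD 1, no drug effect, and baseline-to-last correlation r of 0.5 to 0.9. None of these values is in the documents.

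- *Precision of mean paired change.* Half-width = t(0.975, 14)/√15 × √(2(1−r)), with t = 2.145. At r = 0.5: 2.145/3.873 × 1.000 = 0.55 SDS. At r = 0.9: 0.554 × 0.447 = 0.25 SDS.
- *Background newly-low rate.* This is (q − j)/(1 − q), where q is the probability of being low at one visit and j of being low at both.
  - Mean SDS 0: q = 0.0500. With r = 0.5, j = 0.0122, giving 0.0378/0.9500 = 4.0%. With r = 0.9, j = 0.0319, giving 1.9%.
  - Mean SDS −0.3: q = 0.0893. With r = 0.5, j = 0.0276, giving 0.0617/0.9107 = 6.8%. With r = 0.9, j = 0.0607, giving 3.1%.

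So about 2–7% of children not low at baseline would be newly low with no drug effect at all.

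**The case against.** The strongest reply is that little is hidden. With 15 children, a graph and growth chart for each is a nearly complete paired display. It also shows already-low children who worsen, whom a newly-low count omits. The yearly summary has a Baseline window, and the counts of notably low SDS may give the number low before treatment. This stands: a reader might infer that the plan ignores the pre-drug baseline, and the documents do not support that. What is missing is narrower, namely a summary that pairs the values.

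A reader might also infer that the last-visit rate is wrong. It is not. It is nowhere called incidence or new onset, and it is the measure tied to the 5–10% benchmark and Table 3-1. Protocol section 3 words the objective as monitoring, and its listed primary growth endpoints are height and BMI SDS by year since baseline, not this rate.

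Third, 15 children support little inference, and at one flagged child the candidate intervals overlap almost entirely. That is true and limits the gain to description. All the analyses are primarily descriptive in any case.

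Finally, the SAP refers to TFL shells that were not among the documents, so such a table may already exist there. If so, a sentence in 3.8.1 is enough.

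**Conclusion.** The point holds in a limited form. The growth-abnormality rate cannot separate pre-existing from new low stature, and neither document specifies a paired growth summary that would. Fixed marginal counts of 3 and 3 among 15 leave the newly-low figure anywhere between 0/12 and 3/12. The actual distortion cannot be computed, because the number low at baseline is not given. If 5–10% were low, that is 0.75 to 1.5 children at 6.7 points each.

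Two stronger conclusions should be resisted. A newly-low count would not measure the effect of everolimus: with no drug effect it still has a background of about 2–7%, assuming SD 1, mean SDS 0 to −0.3 and r 0.5–0.9. Nor do the documents support setting it beside TOSCA to supply the missing control. SAP 4.2 rejects comparison at this sample size, and such columns would be unadjusted for age and baseline stature.

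This is a cheap improvement to a valid monitoring analysis.

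**What to change.** Keep the last-visit rate as defined, with its link to Table 3-1. Add to SAP 3.8.1, as descriptive outputs for CRAD001M2305 patients only:

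1. A baseline-by-last shift table of SDS category for height and for BMI: below the 5th percentile, 5th to 95th, above the 95th, missing.
2. The number newly low among patients not low at the pre-everolimus baseline, with an exact 95% interval.
3. Paired change from baseline in height and BMI SDS, by yearly window and at the last visit, with a 95% interval and the number of pairs.

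Do not add TOSCA columns for (2) and (3).

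The cost is a few tables from data already held; no protocol-defined quantity changes. Patients without a pre-drug value drop out of (2) and (3). Already-low children who worsen are missed by (2) and show up only in (3). Precision is low: the half-width for mean change is about 0.25–0.55 SDS if all 15 pairs are available, under the assumptions above. A footnote should say that (2) has a non-zero background rate and does not isolate a drug effect.
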